## **9.0 STUDY MANAGEMENT**

### **9.1 Institutional Review Board (IRB) Approval and Consent**

It is expected that the IRB will have the proper representation and function in accordance with federally mandated regulations. The IRB should approve the consent form and protocol.

In obtaining and documenting informed consent, the investigator should comply with the applicable regulatory requirement(s), and should adhere to Good Clinical Practice (GCP) and to ethical principles that have their origin in the Declaration of Helsinki.

Before recruitment and enrollment onto this study, the patient will be given a full explanation of the study and will be given the opportunity to review the consent form. Each consent form must include all the relevant elements currently required by the FDA Regulations and local or state regulations. Once this essential information has been provided to the patient and the investigator is assured that the patient understands the implications of participating in the study, the patient will be asked to give consent to participate in the study by signing an IRB-approved consent form.

Prior to a patient's participation in the trial, the written informed consent form should be signed and personally dated by the patient and by the person who conducted the informed consent discussion.

## **9.2 Required Documentation**

Before the study can be initiated at any site, the following documentation must be provided to the Clinical Protocol Office (CPO) at the University of North Carolina.

- A copy of the official IRB approval letter for the protocol and informed consent
- IRB membership list
- CVs and medical licensure for the principal investigator and any sub-investigators who will be involved in the study.
- Form FDA 1572 appropriately filled out and signed with appropriate documentation
- Financial Disclosures
- CAP and CLIA Laboratory certification numbers and institution lab normal values
- Executed clinical research contract

## **9.3 Registration Procedures**

All patients must be registered with the CPO at the University of North Carolina before enrollment to study. Prior to registration, eligibility criteria must be confirmed with the UNC Study Coordinator. To register a patient, call the CPO at [contact] Monday-Friday 9:00 am – 5:00 pm EST or email the UNC Project Manager.

## **9.4 Data Management and Monitoring/Auditing**

The CPO of the UNC LCCC will serve as the coordinating center for this trial. Data will be collected through a web based clinical research platform, OnCore®. All data will be collected and entered into OnCore® by research coordinators from UNC LCCC.

As an investigator initiated study, this trial will also be audited by the LCCC compliance committee every six or twelve months.

## **9.5 Adherence to the Protocol**

Except for an emergency situation in which proper care for the protection, safety, and well-being of the study patient requires alternative treatment, the study shall be conducted exactly as described in the approved protocol.

### 9.5.1 Emergency Modifications

UNC investigators may implement a deviation from, or a change of, the protocol to eliminate an immediate hazard(s) to trial subjects without prior UNC or their respective institution's IRB/IEC approval/favorable opinion.

For any such emergency modification implemented, a UNC IRB modification form must be completed by UNC Research Personnel within five (5) business days of making the change.

### 9.5.2 Single Patient/Subject Exceptions

Eligibility single subject exceptions are not permitted for Lineberger Comprehensive Cancer Center Investigator Initiated Trials under any circumstances. Other types of single subject exceptions may be allowed if proper regulatory review has been completed in accordance with Lineberger Comprehensive Cancer Center's Single Subject Exceptions Policy.

### 9.5.3 Other Protocol Deviations/Violations

According to UNC's IRB, a protocol deviation is any unplanned variance from an IRB approved protocol that:

- Is generally noted or recognized after it occurs
- Has no substantive effect on the risks to research participants
- Has no substantive effect on the scientific integrity of the research plan or the value of the data collected
- Did not result from willful or knowing misconduct on the part of the investigator(s).

An unplanned protocol variance is considered a violation if the variance meets any of the following criteria:

- Has harmed or increased the risk of harm to one or more research participants.
- Has damaged the scientific integrity of the data collected for the study.
- Results from willful or knowing misconduct on the part of the investigator(s).
- Demonstrates serious or continuing noncompliance with federal regulations, State laws, or University policies.

If a deviation or violation occurs, please follow the guidelines below:

**Protocol Deviations:** UNC personnel will record the deviation in OnCore®, and report to any sponsor or data and safety monitoring committee in accordance with their policies. Deviations should be summarized and reported to the IRB at the time of continuing review.

**Protocol Violations:** Violations should be reported by UNC personnel within one (1) week of the investigator becoming aware of the event using the same IRB online mechanism used to report Unanticipated Problems.

**Unanticipated Problems:** Any events that meet the criteria for “Unanticipated Problems” as defined by UNC’s IRB must be reported by the study personnel using the IRB’s web-based reporting system.

## 9.6 Amendments to the Protocol

Should amendments to the protocol be required, the amendments will be originated and documented by the Principal Investigator at UNC. It should also be noted that when an amendment to the protocol substantially alters the study design or the potential risk to the patient, a revised consent form might be required. All protocol amendments will be submitted to Amgen for review.

The written amendment, and if required the amended consent form, must be sent to UNC’s IRB for approval prior to implementation.

## 9.7 Record Retention

Study documentation includes all eCRFs, data correction forms or queries, source documents, Sponsor-Investigator correspondence, monitoring logs/letters, and regulatory documents (e.g., protocol and amendments, IRB correspondence and approval, signed patient consent forms).

Source documents include all recordings of observations or notations of clinical activities and all reports and records necessary for the evaluation and reconstruction of the clinical research study.

Government agency regulations and directives require that all study documentation pertaining to the conduct of a clinical trial must be retained by the study investigator. In the case of a study with a drug seeking regulatory approval and marketing, these documents shall be retained for at least two years after the last approval of marketing application in an International Conference on Harmonization (ICH) region. In all other cases, study documents should be kept on file until three years after the completion and final study report of this investigational study.

## 9.8 Obligations of Investigators

The Principal Investigator is responsible for the conduct of the clinical trial at the site in accordance with Title 21 of the Code of Federal Regulations and/or the Declaration of Helsinki. The Principal Investigator is responsible for personally overseeing the treatment of all study patients. The Principal Investigator must assure that all study site personnel, including sub-investigators and other study staff members, adhere to the study protocol and all FDA/GCP/NCI regulations and guidelines regarding clinical trials both during and after study completion.

The Principal Investigator will be responsible for assuring that all the required data will be collected and entered into the eCRFs. Periodically, monitoring visits will be conducted and the Principal Investigator will provide access to his/her original records to permit verification of proper entry of data. At the completion of the study, all eCRFs will be reviewed by the Principal Investigator and will require his/her final signature to verify the accuracy of the data.

## 11.0 APPENDICES

### 11.1 Appendix A: ECOG Performance Status

Score	Definition
0	Fully active, able to carry on all pre-disease performance without restriction
1	Restricted in physically strenuous activity but ambulatory and able to carry out work of a light or sedentary nature, e.g., light hours work, office work
2	Ambulatory and capable of all self-care but unable to carry out any work activities. Up and about more than 50% of waking hours.
3	In bed or chair more than 50% of waking hours
4	Totally confined to bed or chair – cannot carry on any self-care.
5	Dead

## 11.2 Appendix B: Cockcroft-Gault Formula

### Males:

$$\text{Creatinine CL (mL/min)} = \frac{\text{Weight (kg)} \times (140 - \text{Age})}{72 \times \text{serum creatinine (mg/dL)}}$$

### Females:

[figure not shown]
$$\text{Creatinine CL (mL/min)} = \frac{\text{Weight (kg)} \times (140 - \text{Age})}{72 \times \text{serum creatinine (mg/dL)}} \times 0.85$$

### **11.3 Appendix C: Treatment Algorithms for Nivolumab Therapy**

Algorithms are presented for management of GI, renal, hepatic, pulmonary, endocrine, skin and neurological toxicities are provided.

## GI Adverse Event Management Algorithm

[figure not shown]
Rule out non-inflammatory causes. If non-inflammatory cause is identified, treat accordingly and continue I-O therapy. Opiates/narcotics may mask symptoms of perforation. Infliximab should not be used in cases of perforation or sepsis.

Patients on IV steroids may be switched to an equivalent dose of oral corticosteroids (e.g. prednisone) at start of tapering or earlier, once sustained clinical improvement is observed. Lower bioavailability of oral corticosteroids should be taken into account when switching to the equivalent dose of oral corticosteroids.

## Renal Adverse Event Management Algorithm

[figure not shown]
Rule out non-inflammatory causes. If non-inflammatory cause, treat accordingly and continue I-O therapy

Patients on IV steroids may be switched to an equivalent dose of oral corticosteroids (e.g. prednisone) at start of tapering or earlier, once sustained clinical improvement is observed. Lower bioavailability of oral corticosteroids should be taken into account when switching to the equivalent dose of oral corticosteroids.

## Hepatic Adverse Event Management Algorithm

Rule out non-inflammatory causes. If non-inflammatory cause, treat accordingly and continue I-O therapy. Consider imaging for obstruction.

Patients on IV steroids may be switched to an equivalent dose of oral corticosteroids (e.g. prednisone) at start of tapering or earlier, once sustained clinical improvement is observed. Lower bioavailability of oral corticosteroids should be taken into account when switching to the equivalent dose of oral corticosteroids.

[figure not shown]
\*I-O therapy may be delayed rather than discontinued if AST/ALT ≤ 8 x ULN or T.bili ≤ 5 x ULN.

\*\*The recommended starting dose for grade 4 hepatitis is 2 mg/kg/day methylprednisolone IV.

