#### 4.3.2 Nivolumab Dose Modifications/Delays

Toxicity grades per NCI-CTCAE Criteria v5.0

Adverse Reaction	Severity	Dose Modification
Colitis	Grade 2 diarrhea or colitis	Withhold dose a
	Grade 3 diarrhea or colitis	Withhold dose a when administered as a single agent
		Permanently discontinue when administered with ipilimumab
	Grade 4 diarrhea or colitis	Permanently discontinue
Pneumonitis	Grade 2 pneumonitis	Withhold dose a
	Grade 3 or 4 pneumonitis	Permanently discontinue
Hepatitis/non-HCC b	Aspartate aminotransferase (AST)/ or alanine aminotransferase (ALT) more than 3 and up to 5 X the ULN or total bilirubin $> 1.5$ and up to 3X ULN	Withhold dose a
	AST or ALT more than 5X ULN or total bilirubin $> 3X$ ULN	Permanently discontinue
Hepatitis/HCC b	If AST/SLT is within normal limits at baseline and increases to more than 3 and up to 5 times the ULN or total bilirubin more than 1.5 and up to 3 times the ULN	Withhold dose c
	If AST/ALT is more than 1 and up to 3	

	times ULN at baseline and increases to more than 5 and up to 10 times the ULN  If AST/ALT is more than 3 and up to 5 times ULN at baseline and increases to more than 8 and up to 10 times ULN	
	If AST/ALT is more than 3 and up to 5 times ULN at baseline and increases to more than 8 and up to 10 times the ULN	Permanently discontinue
Hypophysitis	Grade 2 or 3 hypophysitis	Withhold dose a
	Grade 4 hypophysitis	Permanently discontinue
Adrenal insufficiency	Grade 2 adrenal insufficiency	Withhold dose a
	Grade 3 or 4 adrenal insufficiency	Permanently discontinue
Type 1 Diabetes Mellitus	Grade 3 hyperglycemia	Withhold dose a
	Grade 4 hyperglycemia	Permanently discontinue
Nephritis and Renal Dysfunction	Serum creatinine more than 1.5 and up to 6X ULN	Withhold dose a
	Serum creatinine more than 6X ULN	Permanently discontinue
Skin	Grade 3 rash or suspected Stevens-Johnson syndrome (SJS) or toxic epidermal necrolysis (TEN)	Withhold dose a
	Grade 4 rash or confirmed SJS or TEN	Permanently discontinue
Encephalitis	New-onset moderate or severe neurologic signs or symptoms	Withhold dose a
	Immune-mediated encephalitis	Permanently discontinue
Other	Other Grade 3 adverse reaction First occurrence	Withhold dose a
	Recurrence of same Grade 3 adverse reaction	Permanently discontinue
	Life-threatening or Grade 4 adverse reaction	Permanently discontinue

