#### 4.3.2.4 Discontinuation Criteria for Nivolumab

Treatment should be permanently discontinued for the following:

- Any Grade 2 drug-related uveitis or eye pain or blurred vision that does not respond to topical therapy and does not improve to Grade 1 severity within the re-treatment period OR requires systemic treatment
- Any Grade 3 non-skin, drug-related adverse event lasting > 7 days, with the following exceptions:
  - Grade 3 drug-related uveitis, pneumonitis, bronchospasm, hypersensitivity reaction, or infusion reaction of any duration requires discontinuation

- Grade 3 drug-related endocrinopathies adequately controlled with only physiologic hormone replacement do not require discontinuation
- Grade 3 drug-related laboratory abnormalities do not require treatment discontinuation except those noted below
- Grade 3 drug-related platelet count decreased > 7 days or associated with bleeding requires discontinuation
- Any drug-related hepatic abnormality that meets the following criteria require discontinuation:
  - AST or ALT > 8 x ULN
  - Total bilirubin > 5 x ULN
  - Concurrent AST or ALT > 3 x ULN and total bilirubin > 2 x ULN
- Any Grade 4 drug-related adverse event or laboratory abnormality, except for the following events which do not require discontinuation:
  - Isolated Grade 4 amylase or lipase abnormalities that are not associated with symptoms or clinical manifestations of pancreatitis and decrease to < Grade 4 within 1 week of onset.
  - Isolated Grade 4 electrolyte imbalances/abnormalities that are not associated with clinical sequelae and are corrected with supplementation/appropriate management within 72 hours of their onset
  - Grade 4 lymphocyte count decreased or white blood cell decreased
  - Grade 4 drug-related endocrinopathy adverse events, such as adrenal insufficiency, ACTH deficiency, hyper- or hypothyroidism, or glucose intolerance, which resolve or are adequately controlled with physiologic hormone replacement (corticosteroids, thyroid hormones) or glucose-controlling agents, respectively, may not require discontinuation after discussion with and approval from the Investigator
- Any dosing interruption lasting > 6 weeks with the following exceptions:

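### Nivolumab's hepatic stopping limits disagree between the section 4.3.2 table, section 4.3.2.4 and the Appendix C footnote

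*Combined protocol and SAP*

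**What the plan says.** Three places set hepatic limits for nivolumab.

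- **Section 4.3.2, dose modification table, hepatitis/non-HCC row.** The dose is withheld at AST or "alanine aminotransferase (ALT) more than 3 and up to 5 X the ULN or total bilirubin" above 1.5 and up to 3 x ULN. It is permanently discontinued at "AST or ALT more than 5X ULN or total bilirubin" above 3 x ULN.
- **Section 4.3.2.4, discontinuation criteria.** The wording is mandatory: "Any drug-related hepatic abnormality that meets the following criteria require discontinuation". The list is "AST or ALT > 8 x ULN", "Total bilirubin > 5 x ULN" and "Concurrent AST or ALT > 3 x ULN and total bilirubin > 2 x ULN". The same section says that other Grade 3 drug-related laboratory abnormalities do not require discontinuation.
- **Section 11.3, Appendix C, hepatic algorithm, asterisk footnote.** "I-O therapy may be delayed rather than discontinued if AST/ALT ≤ 8 x ULN or T.bili ≤ 5 x ULN". The flowchart that carries the asterisk is not shown.

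Two further sections bear on how these interact. Section 4.3.2.2 lets a delayed patient resume once the event settles, but calls for permanent discontinuation when combined Grade 2 AST/ALT and bilirubin values meet discontinuation parameters. Section 4.3.2.3 sends investigators to Appendix C for hepatic events and describes the algorithms as guidance that complements medical judgment.

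**The concern.** Delay and discontinuation are different outcomes: a delayed patient may be given nivolumab again, a discontinued one may not. An investigator with a given pair of liver results should reach one answer.

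Within section 4.3.2 the two rules give different answers for non-HCC patients, in both directions. The values involved are reachable. Section 3.1.6 admits patients with liver metastases at AST/ALT up to 5 x ULN, so a modest drug-related rise passes the table's limit well before it reaches the 8 x limit in 4.3.2.4.

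The Appendix C footnote adds a third version. It says nothing about the concurrent criterion, and it joins its two limits with *or*, so that on a literal reading one acceptable test is enough to permit delay. No sentence in the protocol says which text governs. At stake is possible re-exposure of a patient whom one rule would have stopped for good.

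**Working it through.** No plan figure needs reproducing. The check is a comparison of rules.

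**Inputs.** Let A be AST/ALT and B total bilirubin, both in multiples of ULN, for a drug-related event in a non-HCC patient.

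- Table stop (4.3.2): A > 5 or B > 3.
- Table withhold (4.3.2): 3 < A ≤ 5 or 1.5 < B ≤ 3, when not a stop.
- 4.3.2.4 hepatic stop: A > 8, or B > 5, or (A > 3 and B > 2).
- Footnote, literal: delay if A ≤ 8 or B ≤ 5.
- Footnote, each test held to its own limit: delay if A ≤ 8 and B ≤ 5.

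**Step 1: the two body rules.**

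- Stop in the table but not in 4.3.2.4: (5 < A ≤ 8 and B ≤ 2) or (3 < B ≤ 5 and A ≤ 3).
- Stop in 4.3.2.4 but not in the table: 3 < A ≤ 5 and 2 < B ≤ 3. The table only withholds here.

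**Step 2: the footnote against 4.3.2.4.**

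- Literal *or*: delay overlaps a required stop in three zones: (A > 8, B ≤ 5), (A ≤ 8, B > 5) and (3 < A ≤ 8, 2 < B ≤ 5). The first two also lie wholly inside the table's stop.
- Each test to its own limit: only the third zone remains. It comes from the missing concurrent criterion.

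**Step 3: worked values.**

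| A, B | 4.3.2 table | 4.3.2.4 hepatic criteria | Footnote, literal | Footnote, own limits |
|---|---|---|---|---|
| 6, 1 | stop | none met | delay | delay |
| 1, 4 | stop | none met | delay | delay |
| 4, 2.5 | withhold | stop | delay | delay |
| 12, 1 | stop | stop | delay | no delay |
| 4, 6 | stop | stop | delay | no delay |
| 10, 6 | stop | stop | no delay | no delay |

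**Step 4: what closes the gaps.** On a grid of 861 points (A from 0 to 20, B from 0 to 10, steps of 0.5), the literal footnote overlaps the 4.3.2.4 stop at 264 + 170 + 60 = 494 points. Changing *or* to *and* leaves 60, all from the concurrent criterion. Excluding that criterion as well leaves 0. Against the table's stop, 30 + 28 = 58 points still remain, and these are exactly the first disagreement in Step 1. They close only when the footnote also defers to the table, or when one set of limits is chosen. The counts check the algebra; they say nothing about how often patients have such values.

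**The case against.** The case for leaving the text alone has real force on the footnote.

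- Its limits, 8 and 5, are the exact complements of the two single-test stops in 4.3.2.4. That suggests each limit belongs to its own test, in which case delay at AST/ALT 12 with bilirubin 1 was never permitted.
- The flowchart may restrict the note to a particular grade or box, and its absence from the text is not a fault of the plan.
- A permissive *may* in guidance does not displace a mandatory stop, so a careful investigator would probably follow 4.3.2.4.
- For combined Grade 2 values, 4.3.2.2 already repeats the permanent stop.

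All of this stands. A reader might infer that Appendix C authorises continued nivolumab at AST/ALT above 8 x ULN, or that nothing later prevents resumption once the concurrent criterion is met. The documents do not support either inference as a firm statement. What remains is that the visible footnote omits the concurrent criterion on either reading, and that no sentence states the precedence.

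It can also be said that both body rules are obeyed by stopping whenever either says so. That is a sound way to act, but the protocol does not say it. Because 4.3.2.4 excuses other Grade 3 laboratory abnormalities from discontinuation, a reader relying on that section could continue where the table stops. Neither the missing flowchart nor the guidance label bears on this disagreement.

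Finally, a reader might extend the point to HCC patients. It is left out for them: the HCC withhold and discontinue cells print the same condition (baseline above 3 and up to 5, rising to above 8 and up to 10 x ULN), possibly through table extraction, so no conclusion can be drawn from that row.

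**Conclusion.** The point holds as a low-severity safety text correction. The firmer part is the disagreement within section 4.3.2 for non-HCC patients: isolated AST/ALT above 5 to 8, or isolated bilirubin above 3 to 5, stops nivolumab in the table but meets no hepatic criterion in 4.3.2.4; AST/ALT above 3 to 5 with bilirubin above 2 to 3 does the reverse. The footnote is secondary. Its omission of the concurrent criterion is plain in the visible text, while the two wider zones depend on a literal *or*.

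The conclusion assumes drug-related events and considers the hepatic criteria only; other clauses, such as the Grade 4 rule or investigator judgment, could also lead to a stop. The number of patients affected cannot be derived from the documents. The primary endpoint, sample size, toxicity boundary and dose-limiting toxicity definition are unaffected.

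**What to change.** Make three text changes at the next amendment.

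1. In the Appendix C hepatic footnote, replace the condition with: *only if AST/ALT ≤ 8 x ULN and T.bili ≤ 5 x ULN and no section 4.3.2 discontinuation criterion is met*. Do this with the flowchart in view, so that the asterisked box agrees.
2. Add to section 4.3.2.3: *The discontinuation rules in section 4.3.2 govern over Appendix C.*
3. State in section 4.3.2 that non-HCC patients stop permanently when either the table row or 4.3.2.4 requires it. If the sponsor prefers the 8 x and 5 x limits, it should document the reason, use them in both places and keep the concurrent criterion. The table's tighter stop should not be loosened without a stated basis.

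Under the either-rule version, delay in non-HCC patients remains possible only when A ≤ 5, B ≤ 3 and not both A > 3 and B > 2. This overlaps neither stop rule.

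No procedures are added. There are two costs. The protocol's wording would differ from the algorithm that section 4.3.2.3 says is in the nivolumab investigator's brochure. Some patients with isolated AST/ALT above 5 to 8 x ULN or bilirubin above 3 to 5 x ULN would stop where 4.3.2.4 alone would not require it.
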